6.1.1. Inclusion Criteria

Patients may be included in the study if they meet all of the following criteria during screening prior to first dose of study drug.

- [1] Have a histologically confirmed diagnosis of STS for which olaratumab and doxorubicin would be appropriate therapy. Patients with a diagnosis of Grade 1 liposarcoma are eligible if there is histological or radiographic evidence of evolution to more aggressive disease. Patients with Kaposi's sarcoma and gastrointestinal stromal tumors (GIST) will be excluded. Patients must have potentially resectable disease (as assessed by the study investigator) and have a primary tumor lesion deemed amenable to serial biopsy.
- [2] Have consented to undergo mandatory serial peripheral whole blood and tumor tissue sampling for pathology review and translational research. Refer to Sections [8.2.3.1](#) and [8.2.3.2](#) for details of biopsy and whole blood sample collection.
- [3] Have signed an informed consent form (ICF) and authorization for release of health information for research prior to any study-specific procedures being performed.
- [4] Are age ≥ 18 years at time of consent.
- [5] Have measurable or nonmeasurable but evaluable disease as defined by the Response Evaluation Criteria in Solid Tumors (RECIST v1.1, Eisenhauer et al. 2009). Tumors within a previously irradiated field will be designated as "nontarget" lesions unless progression is documented or a biopsy is obtained to confirm persistence at least 90 days following completion of radiotherapy.
- [6] Have a performance status (PS) of 0 to 1 on the Eastern Cooperative Oncology Group (ECOG) scale (Oken et al. 1982). [Attachment 6](#) provides the ECOG PS scale.

- [7] Have had <2 prior systemic cytotoxic therapies for potentially resectable disease. All previous anticancer treatments must have been completed ≥ 3 weeks (21 days) prior to enrollment.
- [8] Have had resolution of AEs and of all clinically significant toxic effects of prior locoregional therapy, surgery, radiotherapy, or systemic anticancer therapy to Grade ≤ 1 , by National Cancer Institute (NCI)-Common Terminology Criteria for Adverse Events (CTCAE) Version 4.0.
- [9] Have adequate hematologic, organ, coagulation, and cardiac function within 2 weeks (14 days) prior to enrollment:
- Absolute neutrophil count (ANC) $\geq 1.5 \times 10^9/L$. Granulocyte colony-stimulating factor (G-CSF) cannot be administered within 2 weeks (14 days) prior to enrollment.

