10.6. Efficacy

The following secondary efficacy endpoints will be measured:

Progression-free survival (PFS): is defined as the time from enrollment until the first radiographic documentation of objective progression as defined by RECIST (v1.1) ([Attachment 8](#)), or death from any cause. Patients who die without a reported prior progression will be considered to have progressed on the day of their death. Patients who did not progress or who are lost to follow-up will be censored at the day of their last radiographic tumor assessment. If no baseline or postbaseline radiologic assessment is available, the patient will be censored at the date of enrollment. If death or PD occurs after 2 or more consecutive missing radiographic visits, censoring will occur at the date of the last radiographic visit prior to the missed visits. The use of a new anticancer therapy or the performance of a surgical resection prior to the occurrence of PD will result in censoring at the date of last radiographic assessment prior to initiation of new therapy or surgical resection.

3-month PFS: estimated as the total number of patients who did not progress 3 months after enrollment divided by the total number of patients.

Overall response rate (ORR): estimated as the total number of CRs, complete responses unconfirmed (CRus), and PRs divided by the total number of patients.

Disease control rate (DCR): is computed as the total number of patients with the best overall response of CR, CRu, PR, or SD divided by the total number of patients.

Rate of Resectability: is defined as the total number of patients who are resectable (see definition of resectability in Section 4) divided by the total number of patients.

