It is assumed that at each protocol-specified time point, a response assessment occurs. (When no imaging/measurement is done at all at a particular time point, the patient is not evaluable (NE) at that time point.) Table 1 provides a summary of the overall response status calculation at each time point for patients who have *measurable disease* at baseline.

Table 1. Time Point Response: Patients with Target (\pm Nontarget) Disease

Target Lesions	Non-Target Lesions	New Lesions	Overall Response
CR	CR	No	CR
CR	Non-CR/non-PD	No	PR
CR	Not evaluated	No	PR
PR	Non-PD or not all evaluated	No	PR
SD	Non-PD or not all evaluated	No	SD
Not all evaluated	Non-PD	No	NE
PD	Any	Yes or No	PD
Any	PD	Yes or No	PD
Any	Any	Yes	PD

Abbreviations: CR = complete response; PR = partial response; SD = stable disease.; PD = progressive disease; NE = inevaluable.

Table 2 is to be used when patients have *nonmeasurable* disease only.

Table 2. Time Point Response: Patients with Nontarget Disease Only

Nontarget Lesions	New Lesions	Overall Response
CR	No	CR
Non-CR/non-PD	No	Non-CR/non-PD ^a
Not all evaluated	No	NE
Unequivocal PD	Yes or No	PD
Any	Yes	PD

Abbreviations: CR = complete response; PD = progressive disease ; NE = inevaluable.

^a non-CR/non-PD is preferred over SD for nontarget disease.

Frequency of Tumor Re-Evaluation

A baseline tumor evaluation must be performed within 4 weeks before patient begins study treatment. Frequency of tumor re-evaluation while on and adapted to treatment should be protocol-specific and adapted to the type and schedule of treatment. In the context of Phase 2 studies where the beneficial effect therapy is not known, follow-up every 6-8 weeks is reasonable. Normally, all target and non-target sites are evaluated at each assessment using the same method. However, bone scans may need to be repeated only when CR is identified in target disease or when progression in bone is suspected.

Confirmatory Measurement/Duration of Response

Confirmation:

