- **Consolidated AEs** are composite AE terms consisting of synonymous Medical Dictionary for Regulatory Activities (MedDRA) preferred terms (PTs) to allow meaningful interpretation of the AE data. Consolidated AE categories and PTs will be maintained at compound level and reported in the CSR.
- **Serious adverse event (SAE)** is any AE that results in one of the following outcomes:

- death
 - a life-threatening experience (that is, immediate risk of dying)
 - persistent or significant disability/incapacity
 - initial or prolonged in-patient hospitalization
 - congenital anomaly/birth defect
 - considered significant by the investigator for any other reason
- **Treatment-emergent adverse event (TEAE)** is defined as an event that first occurred or worsened in severity after baseline and 30 days after the last dose of study treatment and related SAEs reported beyond 30 days after the last dose of study treatment, where last dose stands for actual dose, that is, 0 dose is not counted as last dose.

Exposure-related variables are listed below:

- **Dose exposures:** As reported in the eCRF
- **Number of dose level reductions:** Sum of the number of dose level reductions as reported in the eCRF
- **Dose delays:** As reported in the eCRF
- **Dose withheld/skip (Not Administered):** As reported in the eCRF
- **Dose interruption:** As reported in the eCRF

5.3.5. *Efficacy Variables*

The study was not designed to make an efficacy assessment. However, any tumor response data will be tabulated according to assigned treatment.

Circulating tumor cells (CTC) will be assessed at pre-olaratumab and post-olaratumab in whole blood.

Secondary efficacy analysis will be performed to investigate antitumor activity by assigned treatment. Response and disease progression will be evaluated using Response Evaluation Criteria in Solid Tumors (RECIST) version 1.1 (Eisenhauer et al. 2009) for all tumors.

Overall Response Rate (ORR) is defined as the percentage of patients achieving a best overall response of either Complete Response (CR), complete responses unconfirmed (CRus) or Partial Response (PR), as determined by RECIST 1.1. The best overall response is the best response from the start of the treatment until PD/recurrence.

Disease control rate (DCR) is defined as the percentage of patients achieving a best overall response of CR, CRu, PR, or SD as determined by RECIST 1.1. Patients who do not have any

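### DCR omits non-CR/non-PD, the code Attachment 8 gives to persistent, non-progressing disease in nontarget-only patients, yet divides by all patients (wrong as written, minor)

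*Protocol*

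**What the plan says.** **DCR.** Protocol 10.6 defines it as "computed as the total number of patients with the best overall response of CR, CRu, PR, or SD", with all patients as the denominator. SAP 5.3.5 has it "defined as the percentage of patients achieving a best overall response of CR, CRu, PR, or SD as determined by RECIST 1.1", and SAP 5.10 repeats the sum CR + CRu + PR + SD with an exact 95% confidence interval. SAP 5.3.5 also keeps patients with no postbaseline assessment in the denominator as non-responders.

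**Population.** Protocol 10.1.2 analyses efficacy on all enrolled patients. SAP Table JGDM.5.2 limits this to those who received investigational product. Neither restricts DCR to patients with measurable disease.

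**Eligibility.** Criterion 5 in Protocol 6.1.1 reads "Have measurable or nonmeasurable but evaluable disease as defined by the Response Evaluation Criteria in Solid Tumors". It also makes tumors in a previously irradiated field nontarget, with two exceptions: documented progression, or a biopsy showing persistence at least 90 days after radiotherapy.

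**Response coding.** Attachment 8 Table 2 applies when a patient has nonmeasurable disease only. Its possible results are CR, non-CR/non-PD, NE and PD. The footnote states that "non-CR/non-PD is preferred over SD for nontarget disease". Attachment 8 says best overall response is derived by an algorithm from the investigator's assessments, but does not set the algorithm out.

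**The concern.** The DCR definition and the response table do not fit together for one eligible group. A patient with nontarget disease only can be followed throughout without progressing and still never receive PR or SD, because Table 2 does not offer them. Unless every lesion disappears, the best available result is non-CR/non-PD, and that result is not in the DCR numerator.

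A rate meant to count patients whose disease is held in check would then leave out some whose disease is held in check, and the error can only go downward. If the mismatch is found at analysis instead, someone must decide how to code these patients with the data in view, in an open-label, single-arm study.

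**Working it through.** **1. The plan's own interval.** The only precision figure in the documents is for the PDGFRα hit rate: 17 of 35, with a 95% interval of 31% to 66% (Protocol 10.1.1). The exact (Clopper-Pearson) interval for 17/35 is 31.4% to 66.0%, so the figure reproduces. No expected rate or precision is stated for DCR. SAP 5.10 specifies an exact interval for DCR, so the same method is used below.

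**2. Table 2 outcomes against the DCR numerator, for a nontarget-only patient**

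| Best overall response | In DCR numerator as written? | In denominator? |
|---|---|---|
| CR | Yes | Yes |
| Non-CR/non-PD | No | Yes |
| NE | No | Yes |
| PD | No | Yes |

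Only the second row is a mismatch. CR counts already, and NE and PD would fail under any sensible definition.

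**3. Formula.** Let N be the number of patients analysed and k the number whose best overall response is non-CR/non-PD and who meet the minimum duration required for SD. Then

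DCR (corrected) − DCR (as written) = k/N.

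With N = 35, the planned enrollment in Protocol 6.2, one patient shifts DCR by 1/35 = 2.9 points.

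**4. Range.** The documents do not give k, so the values below are assumptions. The illustration also assumes that 21 of 35 patients truly have disease control, so the corrected DCR is 21/35 = 60.0% (exact 95% CI 42.1 to 76.1).

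| k (assumed) | DCR as written | Exact 95% CI | Shift |
|---|---|---|---|
| 0 | 21/35 = 60.0% | 42.1 to 76.1 | 0 |
| 1 | 20/35 = 57.1% | 39.4 to 73.7 | 2.9 points |
| 2 | 19/35 = 54.3% | 36.6 to 71.2 | 5.7 points |
| 3 | 18/35 = 51.4% | 34.0 to 68.6 | 8.6 points |

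For scale, the half-width of the interval around 60.0% is (76.1 − 42.1)/2 = 17.0 points. One or two affected patients move the estimate by much less than its sampling uncertainty, but always in the same direction.

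**5. Is there a rescuing rule?** I looked for one in Protocol 5.2.2, 10.1.2, 10.6 and Attachment 8, and in SAP 4.2, 5.3.5, 5.4, 5.5.1 and 5.10. None equates non-CR/non-PD with SD, adds it to DCR, or limits DCR to measurable disease. Footnote b of SAP Table JGDM.5.1 has the same gap: an adequate assessment for PFS is one reading CR, PR, SD or PD, so a non-CR/non-PD scan does not qualify.

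**The case against.** **The coding is not absolute.** The footnote expresses a preference, and the best-response algorithm is not given, so a programmer could map non-CR/non-PD to SD. A reader might infer that these patients are certain to be scored as failures. The documents do not go that far: the result follows from reading the category list and Table 2 literally. The objection stands to that extent. It does not remove the problem, because no mapping is written and the literal reading gives the wrong answer.

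**The group is probably very small.** Criterion 1 requires potentially resectable disease with a primary lesion suitable for serial biopsy, and Protocol 8.2.3.2 requires excisional or core-needle specimens before and after Cycle 1. A lesion is measurable from 10 mm on CT or MRI, so most such primaries should be measurable. The irradiated-field route is narrowed by criterion 5's biopsy exception, since a pretreatment biopsy is mandatory. Attachment 8 has no such exception and requires demonstrated progression, so the route is not closed. This objection stands, and it is why no large effect is claimed.

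**Little depends on DCR.** SAP 5.3.5 says the study was not designed to assess efficacy, and DCR carries no hypothesis or threshold. SAP 5.10 also provides a best-response summary and a listing, so affected patients could be identified and the rate recalculated. This limits the severity. A reported rate should still follow from a definition that is right in itself.

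**Conclusion.** Wrong as written, and minor. Applied literally, the DCR rule counts a nontarget-only patient with persistent, non-progressing disease as not controlled. The firm size is 2.9 points per affected patient at N = 35. It would be slightly less if replacement of nonevaluable patients raises the number analysed. The total is k/N, with k unknown and probably between zero and a few.

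Two stronger readings are tempting and not supported:

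- A reader might infer that DCR is too low by the whole share of patients with nonmeasurable disease only. It is not. Those who reach CR count already and those with PD or NE would not count anyway, so the loss is confined to those whose best response is non-CR/non-PD.
- A reader might infer a loss of many points. No figure in the documents supports any particular count, and the eligibility rules point to a low one.

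The conclusion rests on reading the four listed categories as complete and on the absence of any written mapping to SD. It has no bearing on the primary biomarker objectives or the sample size. The PFS footnote has the same cause and should be treated as part of the same correction, not as an independent error.

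**What to change.** In Protocol 10.6 and SAP 5.3.5 and 5.10, keep the numerator of CR, CRu, PR and SD and add non-CR/non-PD for patients with nontarget disease only. Apply the same minimum that Attachment 8 sets for SD: the criteria met at least once, not less than 6 weeks after first dose. Suggested sentence: *For patients with nontarget disease only at baseline, a best overall response of non-CR/non-PD that meets the minimum interval required for SD counts as disease control.*

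CRu should stay in the numerator. Whether it belongs there is a separate question that this edit should not settle by omission.

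In footnote b of SAP Table JGDM.5.1, add non-CR/non-PD to the results that make an assessment adequate, so that PFS and DCR treat these patients consistently.

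Make the change before the second database lock, when all objectives are evaluated, so that the rule is fixed in advance. The cost is one sentence in each document, a few added words in the footnote and a small programming change. No new data, visits or procedures are needed.

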10.7. Pharmacokinetic Analyses

Pharmacokinetic parameter estimates for olaratumab will be calculated by standard noncompartmental methods of analysis in patients who have received at least 1 dose of olaratumab and have had samples collected. The primary parameters for analysis will be maximum plasma concentration (C_{max}), minimum plasma concentration (C_{min}), area under the plasma concentration-time curve from time zero to the last measurable plasma concentration ($AUC[0-t_{last}]$), and area under the plasma concentration-time curve from time zero to infinity ($AUC[0-\infty]$) of olaratumab, where appropriate. Other noncompartmental parameters, such as half-life ($t_{1/2}$), clearance (CL), and volume of distribution (V_d), may be reported.

Additional exploratory analyses may be performed if warranted by data and other validated PK software programs (for example, NONMEM) may be used if appropriate and approved by Lilly global PK management. The version of any software used for the analysis will be documented and the program will meet the Lilly requirements of software validation.

10.8. Interim Analyses

An interim analysis will be done to look at the biomarker data once approximately half of the evaluable patients complete the second tumor tissue biopsy and C2D1 whole blood draw. The purpose of this interim analysis is to review the biomarker and safety data. If this interim look at the biomarker data warrants any changes in the study conduct, it will be implemented in an appropriate manner (that is, protocol amendment). Section 10.1 describes the 2 database locks and the interim analysis that will occur in this study.

11. Informed Consent, Ethical Review, and Regulatory Considerations

11.1. Informed Consent

The investigator is responsible for ensuring that the patient understands the potential risks and benefits of participating in the study, including answering any questions the patient may have throughout the study and sharing in a timely manner any new information that may be relevant to the patient's willingness to continue his or her participation in the study in a timely manner.

The ICF will be used to explain the potential risks and benefits of study participation to the patient in simple terms before the patient is entered into the study and to document that the patient is satisfied with his or her understanding of the potential risks and benefits of participating in the study and desires to participate in the study.

The investigator is ultimately responsible for ensuring that informed consent is given by each patient or legal representative before the study is started. This includes obtaining the appropriate signatures and dates on the ICF prior to the performance of any protocol procedures and prior to the administration of study drug.

In this protocol, the term "informed consent" includes all consent given by patients or their legal representatives.

11.2. Ethical Review

Lilly or its representatives must approve all ICFs before they are used at investigative sites(s). All ICFs must be compliant with the ICH guideline on GCP.

Documentation of ERB approval of the protocol and the ICF must be provided to Lilly before the study may begin at the investigative site(s). The ERB(s) will review the protocol as required.

The study site's ERBs should be provided with the following:

1. the current IB and updates during the course of the study
2. ICF
3. relevant curricula vitae

11.3. Regulatory Considerations

This study will be conducted in accordance with:

- 1) consensus ethics principles derived from international ethics guidelines, including the Declaration of Helsinki and Council for International Organizations of Medical Sciences (CIOMS) International Ethical Guidelines
- 2) the ICH GCP Guideline [E6]
- 3) applicable laws and regulations.

The investigator or designee will promptly submit the protocol to applicable ERB(s).

Some of the obligations of the sponsor will be assigned to a TPO.

An identification code assigned by the investigator to each patient will be used in lieu of the patient's name to protect the patient's identity when reporting AEs and/or other study-related data.

11.3.1. Investigator Information

Site-specific contact information may be provided in a separate document.

Physicians with a specialty in oncology will participate as investigators in this clinical trial.

11.3.2. Protocol Signatures

The sponsor's responsible medical officer will approve the protocol, confirming that, to the best of his or her knowledge, the protocol accurately describes the planned design and conduct of the study.

After reading the protocol, each principal investigator will sign the protocol signature page and send a copy of the signed page to a Lilly representative.

Attachment 1. Protocol JGDM Study Schedule

Perform procedures as indicated in the following tables for the baseline, treatment, and posttreatment periods, respectively.

All screening/baseline evaluations are performed within 14 days prior to enrollment, unless otherwise specified. Patients who meet all criteria for enrollment will be assigned to receive treatment. After the patient signs the informed consent form, the site will register the patient in the Interactive Web Response System, which is web-based and accessible 24 hours a day.

Baseline Schedule of Activities

Procedure Category	Protocol Sections	Procedure	Study Period		Comments
			Baseline		
			Cycle	BL	
			Visit	0	
			Duration	Up to 14 days (except where noted)	
Relative Day from Enrollment	≤14	≤7			
Study Entry/ Enrollment	11.1	Informed Consent	X (within 28 days of enrollment)		Written informed consent must be obtained prior to any study-specific screening evaluations. For screening purposes, required assessments performed prior to the date of consent may be used provided they are noted exceptions.
	6.1 7.2.3.1.2.4	Inclusion/Exclusion Evaluation and IWRS		X	Patients who meet all criteria for enrollment will be assigned to receive treatment. After the patient signs the ICF, the site will register the patient in the IWRS. After enrollment, patients should receive their first dose of treatment within 72 hours (3 days) whenever possible.
Medical History	8.1.2	Medical History	X		Any preexisting and pretreatment toxicity (treatment- or disease-related) should be documented and recorded as part of the pretreatment medical history. Disease characteristics at initial diagnosis and at study entry will be collected. All adverse events must be recorded after signing the informed consent.
	6.1	Demography	X		Year of birth, sex, and race/ethnicity will be collected at baseline.
	6.1	Prior Treatment Therapies of Underlying Disease	X		Prior treatment includes any treatment for underlying disease, including maintenance therapy. Start and stop dates should be documented as well.
Physical Examination	6.1	Physical Examination		X	Physical examination at baseline includes height, weight, and BSA measurement.
	6.1 Attachment 6	ECOG Performance Status		X	Refer to Attachment 6 for details.
	6.1	Vital Signs		X	Vital signs include blood pressure, pulse, and temperature.
Concomitant Medications	7.5	Concomitant Medications	X		Concomitant medications will be recorded, including any taken within 30 days prior to start of study treatment (C1D1).
Lab/ Diagnostic Tests	6.1.1 Attachment 2	Hematology	X		Screening evaluations done within 7 days prior to enrollment do not have to be repeated. Testing will be performed locally for patient management and centrally for analysis purposes.
	6.1.1 Attachment 2	Serum Chemistry	X		Screening evaluations done within 7 days prior to enrollment do not have to be repeated. Testing will be performed locally for patient management and centrally for analysis purposes.
	6.1.1 Attachment 2	Coagulation Profile	X		Screening evaluations done within 7 days prior to enrollment do not have to be repeated. Testing will be performed locally only.
	Attachment 2	Urinalysis	X		Screening evaluations done within 7 days prior to enrollment do not have to be repeated. Includes a routine UA, and if clinically indicated a microscopic analysis. If routine analysis indicates > 2+ proteinuria, then a 24-hour urine must be collected and must demonstrate ≤ 1000 mg of protein in 24 hours. Testing will be performed locally only.

		Study Period	Baseline		
		Cycle	BL		
		Visit	0		
		Duration	Up to 14 days (except where noted)		
		Relative Day from Enrollment	≤14	≤7	
Procedure Category	Protocol Sections	Procedure			Comments
Lab/ Diagnostic Tests	6.1.1 Attachment 2	Pregnancy Test		X	Serum β-HCG or urine pregnancy test (women of child-bearing potential only) within 7 days prior to enrollment. If the pregnancy test performed for inclusion purposes is positive, confirm by repeating a serum or urine pregnancy test. The results of this test will not be collected on the eCRF. Testing will be performed locally only.
	6.1.1 Attachment 2	FSH		X	Performed only at screening in menopausal women that have experienced spontaneous amenorrhea for 6 to 12 months. To be done for women only when needed to confirm postmenopausal status. Testing will be performed locally only.
	8.2.3	Tumor Tissue Biopsy		X (within 28 days of enrollment)	When submitting a tissue biopsy, sites should examine samples to determine adequacy of tumor tissue using their local laboratory procedures prior to first dose of olaratumab monotherapy. If additional tumor biopsies are collected as part of clinical care, they should be submitted, along with local pathology reports for further analysis (refer to Section 8.2.3 for details).
	8.1.3.1 9.2.2	ECG		X (within 28 days of enrollment)	A single 12-lead ECG is to be obtained within 28 days prior to enrollment (refer to Section 8.1.3.1 and Section 9.2.2 for details). ECGs will be read locally and measurements will be electronically submitted to a central vendor.
	8.1.3.2	Echocardiogram or MUGA Scan		X (within 28 days of enrollment)	Within 28 days prior to enrollment (refer to Section 8.1.3.2 for details).
	8.2.3.3	PET Scan		X (within 28 days of enrollment)	Within 28 days prior to enrollment. PET scans will be read locally by the investigator and sent to a central vendor where the images will be stored.
Efficacy Assessment	Attachment 8	Imaging Studies (CT/MRI) Tumor Assessments (according to RECIST v1.1)		X (within 28 days of enrollment)	Within 28 days prior to enrollment (refer to Attachment 8 for details). CT/MRI scans will be read locally and a scan will also be sent for storage at a central vendor.
Patient Disposition				X	At the time that the patient is discontinued from study participation, information regarding the patient status will be collected.

Abbreviations: β-HCG = beta human chorionic gonadotropin; BL = baseline; BSA = body surface area; C = cycle; CT= computed tomography; D = day; ECG = electrocardiogram; ECOG = Eastern Cooperative Oncology Group; eCRF = electronic case report form; FSH = follicle-stimulating hormone; ICF = informed consent form; IWRS = Interactive Web Response System; MRI = magnetic resonance imaging; MUGA = multi-gated acquisition; PET = positron emission tomography; RECIST = Response Evaluation Criteria in Solid Tumors; UA = urinalysis.

On-Study-Treatment Schedule of Activities

Procedure Category	Protocol Section	Procedure	Study Period		Treatment Period		Comments		
					Olaratumab Monotherapy	Combination Therapy Olaratumab + Doxorubicin			
			Cycle (21-day cycle ±3 days)		1			2-7	
			Relative Day within Cycle (±3 days)		1 ^{a,b}	8 ^a		1 ^{a,b}	8 ^a
Physical Examination	6.1	Physical Examination	X	X	X	X	Physical examination during treatment period includes weight and BSA measurement. Patients should be weighed on D1 and D8 of each cycle and BSA calculated.		
	6.1 Attachment 6	ECOG Performance Status	X		X		Complete prior to treatment infusion. Refer to Attachment 6 for details.		
	6.1	Vital Signs	X	X	X	X	Vital signs include blood pressure, pulse, and temperature. During the Observation Period (initial 2 cycles of olaratumab therapy), collect vital signs 3 times: 
 • within 15 minutes (+5 minutes) prior to olaratumab infusion • within 1 hour (+5 minutes) after completion of the olaratumab infusion • within 1 hour (+5 minutes) after completion of the doxorubicin infusion. Thereafter (Cycles 3+), obtain vital signs 2 times: within 15 minutes (+5 minutes) prior to olaratumab infusion within 1 hour (+5 minutes) after completion of the doxorubicin infusion.		
Lab/ Diagnostic Tests	Attachment 2	Hematology	X	X	X	X	Laboratory assessments may be done within 7 days prior to D1 and D8 of each cycle. See Attachment 2 for details. Testing will be performed locally for patient management and centrally for analysis purposes.		
	Attachment 2	Serum Chemistry	X		X		Laboratory assessments may be done within 7 days prior to D1 of each cycle. See Attachment 2 for details. Testing will be performed locally for patient management and centrally for analysis purposes.		
	Attachment 2	Coagulation Profile	X		X		Perform on D1 every other cycle or as clinically indicated. See Attachment 2 for details. Testing will be performed locally only.		
	Attachment 2	Urinalysis	X		X		Laboratory assessments may be done within 7 days prior to D1 of every other cycle or as clinically indicated. Includes a routine UA, and, if clinically indicated, a microscopic analysis. If routine analysis indicates >2+ proteinuria, then a 24-hour urine must be collected and must demonstrate ≤1000 mg of protein in 24 hours. Testing will be performed locally only.		
	Attachment 2	Pregnancy Test	X		X		Serum β-HCG or urine pregnancy test on D1 of every cycle or per local practice (whichever is of shorter duration). If a pregnancy test performed on D1 of the cycle is positive, confirm with a serum or urine pregnancy test (pregnancy test results are not recorded on the eCRF). If results are positive, the investigator is to consult with the Lilly CRP. Testing will be performed locally only.		
	8.2.2 Attachment 4	PK Samples	See Attachment 4 for specific time points					Whole blood samples collected for olaratumab serum PK measurements.	

Procedure Category	Protocol Section	Procedure	Study Period				Treatment Period				Comments
			Olaratumab Monotherapy		Combination Therapy Olaratumab + Doxorubicin		Olaratumab Monotherapy		Combination Therapy Olaratumab + Doxorubicin		
			1		2-7		1		2-7		
			1 ^{a,b}	8 ^a	1 ^{a,b}	8 ^a	1 ^{a,b}	8 ^a	1 ^{a,b}	8 ^a	
	8.2.5 Attachment 4	Immunogenicity Samples	See Attachment 4 for specific time points				Whole blood samples collected. If a patient experiences an IRR to olaratumab, blood samples for immunogenicity and PK analysis will be taken at the following time points: (1) as soon as possible after the onset of the IRR, (2) at the resolution of the IRR, and (3) 30 (± 3 days) days after onset of the IRR event.				
Lab/ Diagnostic Tests	8.2.4	Pharmacogenetic Whole Blood Sample for DNA storage	X							Whole blood sample collected. It is highly recommended to draw the whole blood sample prior to the first dose (C1D1 at predose); however, it can be collected later during the study if necessary.	
	8.2.3 Attachment 4	Plasma sample for exploratory biomarkers	X		See Attachment 4 for specific time points					Plasma sample collected. C1D1 at predose, C2D1 (combination therapy pre-dose) and at the end of the patient's study treatment. See Section 8.2.3.1 and Attachment 4 for details and specific time points.	
	8.2.3 Attachment 4	Serum sample for exploratory biomarkers	X		See Attachment 4 for specific time points					Serum sample collected. C1D1 at predose, C2D1 (combination therapy pre-dose) and at the end of the patient's study treatment. See Section 8.2.3.1 and Attachment 4 for details and specific time points.	
	8.2.3 Attachment 4	Mandatory Whole Blood Collection for Circulating Tumor Cells	X		See Attachment 4 for specific time points					Collect mandatory peripheral whole blood samples predose at C1D1, C1D8, C2D1, C2D8, and C3D1, and at end of the patient's study treatment or at the time of surgical resection. See Section 8.2.3.1 and Attachment 4 for details.	
	8.2.3	Mandatory Tumor Tissue				X				Mandatory tumor tissue must be collected up to 3 days prior to the first dose of C2D1. When submitting a specimen from a tumor resection after or during combination therapy, sites should examine samples to determine adequacy of tumor tissue using their local laboratory procedures. If additional tumor biopsies are collected as part of clinical care, they should be submitted, along with pathology reports, for further analysis. See Section 8.2.3.2 for details.	
	8.1.3.1	ECG	X			X				Twelve-lead ECGs are to be collected on Day 1 of monotherapy Cycle 1 and on Day 1 of combination therapy Cycles 2-7. Patients who stop doxorubicin prior to Cycle 7 will undergo the same cardiac monitoring assessment. ECGs will be read locally and measurements will be electronically submitted to a central vendor.	
	8.1.3.2	Echocardiogram or MUGA							X	Echocardiograms or MUGA scans must be performed at the end of combination therapy Cycles 5 and 7 and when clinically indicated. After Cycle 7, (resting LVEF ≥50%), perform echocardiograms or MUGA at the 30-day follow-up visit. Patients who stop doxorubicin prior to Cycle 7 will undergo the same cardiac monitoring assessment. For patients with LVEF <50% or other cardiac dysfunction, perform more frequently, if clinically indicated.	
	8.2.3.3	PET Scan				X				Mandatory PET scan must be collected up to 3 days prior to the first dose of C2D1. PET scans will be read locally by the investigator and sent to a central vendor where the images will be stored.	

Procedure Category	Protocol Section	Procedure	Treatment Period				Comments	
			Study Period		Treatment Period			
					Olaratumab Monotherapy	Combination Therapy Olaratumab + Doxorubicin		
			Cycle (21-day cycle ±3 days)		1			2-7
Relative Day within Cycle (± 3 days)		1 ^{ab}	8 ^a	1 ^a	8 ^{ab}			
Efficacy Assessment	Attachment 8	Imaging Studies (CT/MRI) Tumor Assessments (according to RECIST v1.1)			X		Imaging studies and tumor assessments are to be obtained every 6 weeks (up to 7 days before), irrespective of treatment cycles as calculated from enrollment, until documented progression for patients with CR, PR, or SD, and/or for patients who have discontinued study treatment due to toxicity or reasons other than PD. Refer to Attachment 8 for details. CT/MRI scans will be read locally and a scan will also be sent for storage at a central vendor.	
Adverse Events Collection/CTCAE Grading	8.1.2	Toxicity Assessment	X	X	X	X	All AEs considered at least possibly related to study treatment will be followed until resolution, stabilization, or return to baseline, or until deemed irreversible.	
Concomitant Therapy	7.5	Concomitant Medications	X	X	X	X	Concomitant medications will be recorded throughout the treatment period, including those taken during the 30 days after the last dose of all study treatment.	
Premedication	7.2.2	Administer premedication prior to olaratumab treatment	X	X	X	X	Premedicate all patients with the following medications (or equivalent): a histamine H1 antagonist (eg, diphenhydramine) and dexamethasone intravenously 30–60 minutes prior to the olaratumab doses on Days 1 and 8 of Cycle 1. For subsequent cycles, premedicate all patients with a histamine H1 antagonist (eg, diphenhydramine) intravenously 30-60 minutes prior to each dose of olaratumab.	
	7.2.2	Administer dexrazoxane prior to doxorubicin			X		Dexrazoxane is recommended for all patients receiving 5 or more cycles of doxorubicin.	
Study Treatment	7.1.2	Administer olaratumab	X	X	X	X	Administer through completion of Cycle 7 or until PD, surgical resection, unacceptable toxicity, death, or other withdrawal criteria are met.	
	7.1.3	Administer doxorubicin			X		Administered to all patients during combination therapy for up to a maximum of 6 cycles (Cycles 2-7) (unless previous unacceptable toxicity).	
Patient Disposition			X		X		At the time that the patient is discontinued from any component of the study treatment or study participation, information regarding the patient status will be collected.	

Abbreviations: β -HCG = beta human chorionic gonadotropin; AE = adverse event; BSA = body surface area; C = cycle; CR = complete response; CRP = clinical research physician; CT = computed tomography; CTCAE = Common Terminology Criteria for Adverse Events; D = day; DNA = deoxyribonucleic acid; ECG = electrocardiogram; ECOG = Eastern Cooperative Oncology Group; eCRF = electronic case report form; IRR = infusion-related reaction; LVEF = left ventricular ejection fraction; MRI = magnetic resonance imaging; MUGA = multi-gated acquisition; PD = progressive disease; PET = positron emission tomography; PK = pharmacokinetic; PR = partial response; RECIST = Response Evaluation Criteria in Solid Tumors; SD = stable disease; UA = urinalysis.

- a Study procedures will be performed prior to study drug administration, except where noted (such as vital signs). In case of dose interruption, these evaluations will also be done at minimum frequency every 21 days (± 3 days).
- b Relative day within each cycle (≤ 3 days). Procedure allowed up to 3 days before D1.

Posttreatment Discontinuation Follow-Up Schedule of Activities

Procedure Category	Protocol Section	Procedure	Posttreatment Discontinuation Follow-Up		Comments
			Study Period		
			Short-Term Follow-Up	Long-Term Follow-Up	
			Visit		
